8.1 Discontinuation Criteria of Nivolumab and Ipilimumab

Nivolumab and Ipilimumab administration should be discontinued for the following:

- Any Grade ≥ 2 drug-related uveitis, eye pain, or blurred vision that does not respond to topical therapy and does not improve to Grade 1 severity within the re-treatment period OR requires systemic treatment
- Any Grade 3 non-skin, drug-related adverse event lasting > 7 days, with the following exceptions for laboratory abnormalities, drug-related bronchospasm, hypersensitivity reactions, and infusion reactions:
 - Grade 3 drug-related laboratory abnormalities do not require treatment discontinuation except:
 - Grade 3 drug-related thrombocytopenia > 7 days or associated with bleeding requires discontinuation.
 - Any drug-related liver function test (LFT) abnormality that meets the following criteria require discontinuation:
 - AST or ALT $> 5-10x$ ULN for > 2 weeks
 - AST or ALT $> 10x$ ULN
 - Total bilirubin $> 5x$ ULN
 - Concurrent AST or ALT $> 3x$ ULN and total bilirubin $> 2x$ ULN
 - Grade 3 drug-related bronchospasm, hypersensitivity reaction, or infusion reaction of any duration requires discontinuation

- Any Grade 4 drug-related adverse event or laboratory abnormality, except for the following events which do not require discontinuation:
 - Grade 4 neutropenia ≤ 7 days
 - Grade 4 lymphopenia or leukopenia
 - Isolated Grade 4 electrolyte imbalances/abnormalities that are not associated with clinical sequelae and are corrected with supplementation/appropriate management within 72 hours of their onset.
- Any Grade 4 drug-related adverse event or laboratory abnormality, except for the following events which do not require discontinuation:
 - Grade 4 amylase or lipase abnormalities that are not associated with symptoms or clinical manifestations of pancreatitis. It is recommended to consult with the PI for Grade 4 amylase or lipase abnormalities.
- Any dosing interruption lasting > 6 weeks with the following exceptions:
 - Dosing interruptions to allow for prolonged steroid tapers to manage drug-related adverse events are allowed. Prior to re-initiating treatment in a subject with a dosing interruption lasting > 6 weeks, the principle investigator must be consulted. Tumor assessments should continue as per protocol even if dosing is interrupted.

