 - Dosing interruptions > 6 weeks that occur for non-drug-related reasons may be allowed if approved by the principle investigator. Prior to re-initiating treatment in a subject with a dosing interruption lasting > 6 weeks, the UTMDACC IND Office must be notified. Tumor assessments should continue as per protocol even if dosing is interrupted.
- Any adverse event, laboratory abnormality, or inter-current illness which, in the judgment of the Investigator, presents a substantial clinical risk to the subject with continued nivolumab dosing.
- Any Grade 3 drug-related laboratory abnormality, with the following exceptions for asymptomatic amylase or lipase, AST, ALT, or total bilirubin: Grade 3 amylase or lipase abnormalities that are not associated with symptoms or clinical manifestations of pancreatitis do not require a dose delay. It is recommended to consult with the PI for Grade 3 amylase or lipase abnormalities.
- Any Grade 3 colitis, neurologic toxicity, symptomatic pancreatitis, or pneumonitis.
- Any Grade ≥ 3 Stevens-Johnson Syndrome of Toxic Epidermal Necrolysis(TEN).

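### Section 8.1 gives opposite discontinuation instructions for grade 3 laboratory abnormalities such as short thrombocytopenia, neutropenia and lymphopenia

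*Combined protocol and SAP*

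**What the plan says.** Every entry in Section 8.1 hangs from one opening instruction to discontinue both drugs. Four entries matter here.

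- **Grade 3, by duration.** Treatment stops for "Any Grade 3 non-skin, drug-related adverse event lasting > 7 days", with exceptions. One of these is the sentence "Grade 3 drug-related laboratory abnormalities do not require treatment discontinuation except". Two things follow it: "Grade 3 drug-related thrombocytopenia > 7 days or associated with bleeding requires discontinuation", and a set of AST, ALT and bilirubin thresholds.
- **Grade 3, laboratory.** Further down the list stands "Any Grade 3 drug-related laboratory abnormality, with the following exceptions for asymptomatic amylase or lipase, AST, ALT, or total bilirubin". Of the analytes named there, only amylase and lipase get an explanation: without signs of pancreatitis, grade 3 values "do not require a dose delay".
- **Grade 4, first entry.** "Any Grade 4 drug-related adverse event or laboratory abnormality, except for the following events which do not require discontinuation": neutropenia of up to 7 days; "Grade 4 lymphopenia or leukopenia"; and isolated electrolyte disturbances without clinical consequences that are corrected within 72 hours.
- **Grade 4, second entry.** The same lead sentence is repeated with a single, different exception: "Grade 4 amylase or lipase abnormalities that are not associated with symptoms or clinical manifestations of pancreatitis".

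Sections 8.0 and 8.1 also let the investigator stop treatment on judgement of risk.

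**The concern.** This is an operative safety rule in a trial whose primary objective is safety, and it should give one answer for one laboratory result. Here, one line keeps the patient on drug and another in the same list stops it. Two patients with the same value could be handled differently. A patient could also be stopped for a grade 3 value in an analyte that the first grade 4 entry tolerates at grade 4. The occasion recurs: the schedules in Section 10.0 (note f, both arms) call for blood counts and chemistry on every post-surgical dosing day, and Section 5.3 allows adjuvant treatment for up to 2 years.

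**Working it through.** The plan gives no figure to reproduce. The check is to put the same result through each entry of Section 8.1.

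| Drug-related result | Early grade 3 laboratory sentence | Later grade 3 laboratory entry | Agree? |
|---|---|---|---|
| Thrombocytopenia, grade 3, 3 days, no bleeding | continue | discontinue | no |
| Thrombocytopenia, grade 3, over 7 days or bleeding | discontinue | discontinue | yes |
| Lymphopenia, grade 3 | continue | discontinue | no |
| Neutropenia, grade 3 | continue | discontinue | no |
| Electrolyte abnormality, grade 3 | continue | discontinue | no |
| Amylase or lipase, grade 3, asymptomatic | continue | excepted | yes |
| AST, ALT or bilirubin, grade 3 | stop only at listed thresholds | excepted, no terms given | can be reconciled |

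The conflict is therefore confined to grade 3 values outside amylase/lipase, AST, ALT and total bilirubin and, for platelets, to short episodes without bleeding.

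**Does the nesting remove the conflict?** The early sentence sits under the 7-day entry and could be read as an exception to that entry alone. The later entry would then still stop grade 3 thrombocytopenia of any duration, and the early text's duration-or-bleeding condition for platelets would do nothing. The sentence would keep some effect for the analytes that the later entry excepts. So this reading does not reconcile the two lines for platelets.

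**Grade order.** For lymphopenia, the later entry stops at grade 3, while the first grade 4 entry exempts grade 4. The same holds for neutropenia when the grade 4 episode lasts 7 days or less. On those two lines the milder result is treated more strictly.

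**The duplicated grade 4 criterion.** The first entry has 3 exceptions and the second has 1. None is shared, so there are 3 + 1 = 4 in all. Read literally, each entry stops treatment for anything outside its own exceptions:

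- short neutropenia, lymphopenia/leukopenia and corrected electrolyte disturbances are exempt in the first entry but stopped by the second;
- asymptomatic amylase or lipase is exempt in the second entry but stopped by the first.

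All four exemptions are cancelled. The natural intention is one list of four, but the text does not say so.

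**The case against.** The best defence is that the later laboratory entry is really a hold. Section 8.1 does not say that drug is stopped permanently. The action-taken items in Section 10.3.1.5 separate temporary from permanent discontinuation, and Section 6.1.5 says so explicitly when it means permanent. The entry's own explanation speaks of delay. On that reading, short grade 3 thrombocytopenia is held, and treatment is discontinued only if it is prolonged or there is bleeding. This is plausible and is probably what was meant, but it has to be inferred: the entry stands in the discontinuation list under the same instruction as the rest. The point supports the repair and means that permanent loss of adjuvant treatment should not be presented as the certain result.

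The investigator-judgement stops do not settle the matter. They add reasons to stop and do not say which laboratory rule applies. Following the stricter line throughout would be workable, but nothing visible instructs it.

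A reader might infer three stronger points that the documents do not support.

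- **That Section 7.0 contradicts Section 8.1.** Section 7.0 withholds the next pre-operative dose when a drug-related event of grade 3 or more has not responded to steroids within 2 weeks. It nowhere says that responders may be redosed, so both sections can be obeyed by applying every stop. Section 7.0 also refers to the Appendix I flowcharts, which are not visible here. With enrolment stopped, its pre-operative scope is largely spent.
- **That the conflict changes the 13-of-15 success count in Section 12.2.1.** That rule turns on adverse events that delay surgery, and the plan does not say that a missed dose means assigned therapy was not received.
- **That three of the four grade 4 exemptions are inverted at grade 3.** That count assumes the merged grade 4 list, which is not written. The comparison is secure only against the first grade 4 entry.

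**Conclusion.** The contradiction within Section 8.1 is real and lies wholly in visible text, so it does not depend on the missing flowcharts. It covers grade 3 drug-related laboratory abnormalities other than amylase/lipase, AST, ALT and total bilirubin, and excludes thrombocytopenia that is prolonged or bleeding, where both lines stop treatment. The duplicated grade 4 criterion is a second inconsistency in the same list. The conclusion assumes that the later laboratory entry means what its place in the list says. If it was meant as a hold, the error is one of labelling, and the same repair applies.

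The size cannot be given as a number of patients. The documents do not say how often such values occur or how many patients remain on treatment. This is worth fixing because it is a safety rule that staff must apply to individual results and because the repair is small.

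**What to change.** In Section 8.1:

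1. Keep the early grade 3 laboratory rule, with its thrombocytopenia and liver conditions, as the only grade 3 laboratory criterion for discontinuation.
2. Relabel the later laboratory entry as a dose-delay criterion, or delete it. The investigator should confirm which was intended.
3. Merge the two grade 4 entries into one that carries all four exceptions.

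This costs a few sentences and no new assessments. The downside is that some grade 3 laboratory events are then left to a dose hold or to the investigator-risk stop instead of an automatic discontinuation.

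As an optional clarification, not the correction of an error, Section 7.0 could state that the Section 8.1 stops apply in addition to the steroid-response rule.

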7.0 DOSE MODIFICATIONS

Based upon toxicity profiles on past clinical trials (e.g. nivolumab plus ipilimumab in melanoma [43, 44]), the doses of nivolumab and ipilimumab proposed in this protocol are within the maximum tolerated doses. Therefore, dose reductions or modifications of nivolumab and/or ipilimumab will not be allowed.

For detailed management of toxicities related to nivolumab or ipilimumab, please refer to Appendix 1 (AE I-O Algorithms). If a patient experiences a grade 3 or greater drug-related adverse event after a dose of nivolumab or ipilimumab, and did not respond to steroid treatment within 2 weeks (i.e. improve from G4 to \leq G3; or from G3 to \leq G2), then the next dose will not be administered and the patient will proceed to surgery after the adverse event has resolved or been ameliorated sufficiently so that the patient can proceed safely to surgery. If a patient experiences a grade 3 or greater non-drug related adverse event after a dose of nivolumab or ipilimumab then the patient may receive additional doses of nivolumab or ipilimumab, at the discretion of the PI, if the grade 3 or greater event has resolved or has been reduced sufficiently as assessed by the treating PI prior to administration of the additional doses of nivolumab or ipilimumab.

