AFP = alpha fetoprotein; aPTT = activated partial thromboplastin time; Anti-HBc (total) = Total hepatitis B core antibody; Anti-HDV = hepatitis D virus antibody (previously known as 'delta'); anti-HBs = hepatitis B surface antibody; BP = blood pressure; CBC = complete blood count; Discon = discontinuation; ECOG = Eastern Cooperative Oncology Group; FT4 = free thyroxine; HBeAb or anti-HBe = hepatitis B e antibody; HBeAg = hepatitis B e antigen; HBV = hepatitis B virus; HBcAg = hepatitis B core antigen; HBsAb = hepatitis B surface antibody; HBsAg = hepatitis B surface antigen; HCV = hepatitis C virus; HCV Ab = hepatitis C antibody; INR = international normalized ratio; P = pulse; Q12W = every 12 weeks; RR = respiratory rate; T = temperature; PT = prothrombin time; T3 = triiodothyronine; TSH = thyroid-stimulating hormone, ACTH = adrenocorticotropic hormone .

- a. In subjects that experience site-assessed PD or start a new anti-cancer therapy, contact should be made (example; by telephone) q12W to assess for survival status.
- b. Cycle 1 treatment must be given within 3 days of allocation. The window for each visit is ± 3 days until the end of treatment and ± 7 days during follow-up. Nivolumab is given every 4 weeks after surgery.
- c. Height will be measured at Visit 1 only.
- d. For women of reproductive potential, a urine or serum pregnancy test should be performed within 24 hours prior to C1D1, C5D1 and 30 days post treatment. May use screening pregnancy test if performed within 24 hours of first dose. A serum test can be done if urine is not appropriate. Additionally, if urine test is positive or is not evaluable, a serum test is required. Subjects must be excluded/discontinued in the event of a positive test results. Pregnancy tests (serum and/or urine tests) should be repeated if required by local guidelines.
- e. ECOG Performance Status and laboratory tests for screening and determining eligibility are to be performed within 28 days prior to the first dose of trial treatment.
- f. CBC with differential and chemistry to be performed every 2 weeks before surgery. After surgery, CBC with differential and chemistry are performed on every nivolumab administration day.
- g. Urinalysis and thyroid/hormonal function tests will be performed at every cycle before surgery, at time of surgery (C4D1), at C6D1 and at every restaging thereafter (q12 weeks).

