- Event description
- Date of onset of AE
- CTCAE grade/severity (1, 2, 3, 4, 5)
- Relationship to treatment with nivolumab or ipilimumab (unrelated, unlikely, possible, probable, highly probable/definite)
- Action taken (none, temporarily discontinued agent, drug treatment given/specify, permanently discontinued agent, non-drug treatment given/specify, hospitalization)
- Date of AE stop
- Outcome (recovered without sequelae, recovered with sequelae, ongoing, worsened, death)
- Serious AE (yes, no)
- Serious Adverse Events (SAEs) must be collected from the time of the first protocol specific intervention until 100 days after the last dose of study drug.

Potential Drug Induced Liver Injury (DILI)

Wherever possible, timely confirmation of initial liver-related laboratory abnormalities should occur prior to the reporting of a potential DILI event. All occurrences of potential DILIs, meeting the defined criteria, must be reported as SAEs.

Potential drug induced liver injury is defined as:

- 1) AT (ALT or AST) elevation > 3 times upper limit of normal (ULN)

AND

- 2) Total bilirubin > 2 times ULN, without initial findings of cholestasis (elevated serum alkaline phosphatase),

AND

- 3) No other immediately apparent possible causes of AT elevation and hyperbilirubinemia, including, but not limited to, viral hepatitis, pre-existing chronic or acute liver disease, or the administration of other drug(s) known to be hepatotoxic.

Recommended Adverse Event Recording Guidelines

Attribution	Grade 1	Grade 2	Grade 3	Grade 4	Grade 5
Unrelated	Phase I	Phase I	Phase I	Phase I	Phase I
			Phase II	Phase II	Phase II
				Phase III	Phase III
Unlikely	Phase I	Phase I	Phase I	Phase I	Phase I
			Phase II	Phase II	Phase II
				Phase III	Phase III
Possible	Phase I	Phase I	Phase I	Phase I	Phase I
	Phase II	Phase II	Phase II	Phase II	Phase II
		Phase III	Phase III	Phase III	Phase III
Probable	Phase I	Phase I	Phase I	Phase I	Phase I
	Phase II	Phase II	Phase II	Phase II	Phase II
		Phase III	Phase III	Phase III	Phase III
Definitive	Phase I	Phase I	Phase I	Phase I	Phase I
	Phase II	Phase II	Phase II	Phase II	Phase II
		Phase III	Phase III	Phase III	Phase III

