Appendix I: AE I-O Algorithms

GI Adverse Event Management Algorithm

[figure not shown]
Rule out non-inflammatory causes. If non-inflammatory cause is identified, treat accordingly and continue I-O therapy. Opiates/narcotics may mask symptoms of perforation. Infliximab should not be used in cases of perforation or sepsis.

Patients on IV steroids may be switched to an equivalent dose of oral corticosteroids (e.g. prednisone) at start of tapering or earlier, once sustained clinical improvement is observed. Lower bioavailability of oral corticosteroids should be taken into account when switching to the equivalent dose of oral corticosteroids.

Renal Adverse Event Management Algorithm

[figure not shown]
Rule out non-inflammatory causes. If non-inflammatory cause, treat accordingly and continue I-O therapy

Patients on IV steroids may be switched to an equivalent dose of oral corticosteroids (e.g. prednisone) at start of tapering or earlier, once sustained clinical improvement is observed. Lower bioavailability of oral corticosteroids should be taken into account when switching to the equivalent dose of oral corticosteroids.

Pulmonary Adverse Event Management Algorithm

[figure not shown]
Rule out non-inflammatory causes. If non-inflammatory cause, treat accordingly and continue I-O therapy. Evaluate with imaging and pulmonary consultation.

Patients on IV steroids may be switched to an equivalent dose of oral corticosteroids (e.g. prednisone) at start of tapering or earlier, once sustained clinical improvement is observed. Lower bioavailability of oral corticosteroids should be taken into account when switching to the equivalent dose of oral corticosteroids.

Hepatic Adverse Event Management Algorithm

Rule out non-inflammatory causes. If non-inflammatory cause, treat accordingly and continue I-O therapy. Consider imaging for obstruction.

[figure not shown]
Patients on IV steroids may be switched to an equivalent dose of oral corticosteroids (e.g. prednisone) at start of tapering or earlier, once sustained clinical improvement is observed. Lower bioavailability of oral corticosteroids should be taken into account when switching to the equivalent dose of oral corticosteroids.

*I-O therapy may be delayed rather than discontinued if AST/ALT ≤ 8 x ULN or T.bili ≤ 5 x ULN.

**The recommended starting dose for grade 4 hepatitis is 2 mg/kg/day methylprednisolone IV.

Endocrinopathy Management Algorithm

[figure not shown]

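### Section 8.1 requires stopping drug for concurrent AST/ALT and bilirubin elevations that the Appendix I hepatic footnote lets sites delay, and neither text says which governs

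*Combined protocol and SAP*

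**What the plan says.** Section 8.1 states a mandatory rule: "Any drug-related liver function test (LFT) abnormality that meets the following criteria require discontinuation". Four criteria follow:

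- "AST or ALT $> 5-10x$ ULN for > 2 weeks"
- AST or ALT above 10 times ULN, with no duration attached
- total bilirubin above 5 times ULN
- "Concurrent AST or ALT $> 3x$ ULN and total bilirubin $> 2x$ ULN"

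Section 7.0 directs sites elsewhere for the practical handling of toxicity: "For detailed management of toxicities related to nivolumab or ipilimumab, please refer to Appendix 1 (AE I-O Algorithms". In that appendix, a footnote to the hepatic algorithm reads: "I-O therapy may be delayed rather than discontinued if AST/ALT ≤ 8 x ULN or T.bili ≤ 5 x ULN".

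Section 8.1 does not cite Appendix I, and the visible text of Appendix I does not cite Section 8.1. One later bullet in Section 8.1 also names the liver tests: "Any Grade 3 drug-related laboratory abnormality, with the following exceptions for asymptomatic amylase or lipase, AST, ALT, or total bilirubin". It treats AST, ALT and bilirubin as exceptions but gives no cut-offs for them and no order of precedence.

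**The concern.** A site that has followed Section 7.0 to the appendix meets wording that reads as an exception to discontinuation. If it uses that exception for a patient who meets a Section 8.1 criterion, the patient stays eligible for re-dosing when the protocol body says treatment must end. Delay can lead to re-dosing in this protocol: Section 8.1 lets even interruptions beyond six weeks be followed by re-initiation when they were needed for a steroid taper, after consultation with the principal investigator.

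The concurrent pattern matters most. Section 10.3.1.5 uses the same two thresholds, AST or ALT above 3 times ULN and bilirubin above 2 times ULN, in its definition of potential drug-induced liver injury, subject to conditions on cholestasis and alternative causes. Section 4.1 admits patients with AST or ALT up to 5 times ULN. Some may therefore start above the enzyme half of that threshold, and a modest drug-related rise can take others into the range above 5 times ULN. Section 5.3 allows adjuvant dosing for up to two years, so the end of enrollment did not by itself end exposure. What is at stake is patient safety during treatment.

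**Working it through.** There is no planned figure to reproduce. The check sets the two rules side by side as regions.

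**Inputs.** Let A be AST or ALT and B total bilirubin, both in multiples of ULN, and d the duration in days.

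Section 8.1 requires stopping if any of these holds:

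- C1: 5 < A ≤ 10 and d > 14
- C2: A > 10
- C3: B > 5
- C4: A > 3 and B > 2

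The footnote allows delay if A ≤ 8 or B ≤ 5. The narrower reading, which requires A ≤ 8 and B ≤ 5 together, is used first because it is the least favorable to finding a conflict.

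**Overlap on the narrower reading.**

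- C1 with footnote: 5 < A ≤ 8, B ≤ 5, d > 14. Overlap.
- C2 with footnote: A > 10 and A ≤ 8. Empty.
- C3 with footnote: B > 5 and B ≤ 5. Empty.
- C4 with footnote: 3 < A ≤ 8, 2 < B ≤ 5, any d. Overlap.

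A grid over A from 0 to 20 and B from 0 to 10 in steps of 0.1, at d = 3, 14, 15 and 21, gave exactly these two regions with 0 mismatches. Spot values:

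| A | B | d | Section 8.1 | Footnote, both limits |
|---|---|---|---|---|
| 4 | 3 | 3 | stop (C4) | delay allowed |
| 3.1 | 2.1 | 3 | stop (C4) | delay allowed |
| 8 | 5 | 3 | stop (C4) | delay allowed |
| 8 | 5.1 | 3 | stop (C3, C4) | not allowed |
| 7 | 1 | 21 | stop (C1) | delay allowed |
| 8.1 | 1 | 15 | stop (C1) | not allowed |
| 6 | 1 | 14 | no stop | delay allowed |

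**The two overlaps differ in strength.** C4 has no time element, so both texts apply to the same result on the same day and give different answers. C1 depends on duration. At A = 6, B = 1, d = 14 nothing in C1 is met and delay is consistent with both texts; from day 15 Section 8.1 requires stopping. Delaying first and stopping after two weeks is a coherent sequence, so the conflict exists only if the site still relies on the footnote after day 14.

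Section 7.0 narrows C1 further. If a drug-related event of grade 3 or higher has not responded to steroids within two weeks, the next dose is withheld and the patient goes on to surgery once it is safe. Section 8.1 places its liver list under its Grade 3 laboratory entry, so this rule partly covers presurgical doses. It is framed around surgery and does not settle adjuvant doses.

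**Check of the remedy.** If the footnote applies only to patients who meet none of C1 to C4, its overlap with the stop rule is empty by construction on either reading. Changing its *or* to *and* is not needed for this and has a side effect: A = 9, B = 1, d = 3 meets no Section 8.1 criterion and may be delayed as the footnote now reads (B ≤ 5), but would lose that option because 9 > 8.

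**The case against.** The strongest objection is that the footnote belongs to a flow chart that is not shown. The box it annotates may carry a grade, duration or recovery condition that narrows or removes the overlap. This stands as a limit on confidence. The footnote's own words contain no such condition, and the proposed edits do no harm if the chart already has one.

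Second, Section 8.1 is the study-specific list and is mandatory, while the footnote is permissive. A careful reader would let the mandatory rule win, and a site that stops complies with both texts. That also stands, so the two rules can both be obeyed. But the footnote is phrased as an alternative to discontinuation, in the appendix that Section 7.0 tells sites to use, and no visible text says that the stricter rule prevails.

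Third, there are safeguards. Events meeting the potential liver-injury definition must be reported as serious, to the IND Office within 5 working days (Section 11.1) and to the supporting company within 24 hours (Section 11.3). Sections 8.0 and 8.1 also require stopping on the investigator's judgment of risk. These make unnoticed re-dosing less likely, but they do not rank the two rules.

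A reader might also infer that all four criteria conflict. Taken literally, the *or* does produce that: A = 12 with B = 1 meets C2 and has B ≤ 5; A = 4 with B = 6 meets C3 and has A ≤ 8. The documents do not support resting the point on this. Read alone, the *or* would allow delay at any enzyme level when bilirubin is at or below 5 times ULN, which suggests that the unseen chart supplies limits.

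**Conclusion.** The concern holds as a missing order of precedence between two current texts. On the narrower reading, two of the four Section 8.1 liver criteria are affected. One is a plain same-day conflict (AST/ALT above 3 and up to 8 times ULN with bilirubin above 2 and up to 5 times ULN). The other is secondary (AST/ALT above 5 and up to 8 times ULN for more than two weeks with bilirubin at or below 5 times ULN), mainly in adjuvant dosing.

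This assumes that the footnote means what its words say, with no further condition in the missing chart. The documents do not say how often these patterns arise or whether anyone is still on treatment, so no rate is claimed.

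A reader might infer that patients were re-dosed against Section 8.1, or that the safety results are compromised. Nothing in the documents shows either. No sample size, probability or interval in Section 12 is computed from these thresholds, and no effect on the endpoints or statistics is claimed. The point is a low-cost safety clarification.

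**What to change.** Make two wording changes:

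1. Add to Section 8.1: *The Section 8.1 criteria govern discontinuation; where Appendix I differs, Section 8.1 applies.*
2. Preface the hepatic footnote in Appendix I with: *In patients who meet no Section 8.1 criterion,*

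Leave the footnote's *or* as it stands unless the sponsor's clinicians review it against the flow chart. No extra listing or analysis is needed, since it would not settle which rule applies. The cost is two short edits in an amendment, with no new data, visits or tests.
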